9.4.2 Sample Size Justification

No sample size calculation because a number of 100 cases per study arm was pre-defined by the regulatory body.

9.4.3 Interim Analyses

No interim analysis is planned. Retrospective data up to five years will be analyzed.

9.4.4 Analysis Population

Per Protocol Population: The study population will include all non-censored subjects who have received the Triathlon total knee system cemented with Simplex HV and are available for objective analysis.

The objective analyses will be based on the per protocol population.

Safety Population: The safety population will include all non-censored subjects who received the Triathlon total knee system cemented with Simplex HV.

The safety analysis will be based on the safety population.

10 Study Monitoring, Auditing, and Inspecting

10.1 Study Monitoring Plan

Monitors/Clinical Research Associates (CRAs) are persons employed by sponsors to review the conduct of clinical studies to assure that the clinical investigators abide by their obligations to conduct clinical studies properly. Proper monitoring ensures adequate protection of the rights of human subjects, the safety of subjects involved in a clinical investigation and the quality and integrity of data submitted as a result of the investigation.

This study will be monitored after documentation of retrospective data is done. The investigator will allocate adequate time for such monitoring activities. The investigator will also ensure that the

Monitor/CRA or other compliance or quality assurance reviewer is given access to all study-related documents and study-related facilities, as applicable, and has adequate space to conduct the monitoring visit, when applicable. The Monitor/CRA will review all source documents and compare them to the data contained in the CRFs, in addition to performing a review of regulatory documents such as EC/IRB approvals. The Monitors/CRAs will need the following:

- An area where they can review study data, when monitoring is conducted on site
- Access to CRF data for all cases
- Access to source documentation
- Regulatory documents
- Time to discuss findings with the SC and the investigator

10.2 Auditing and Inspecting

A quality assurance audit is a form of review that provides additional confidence to the sponsor concerning the validity and accuracy of clinical study data that must be submitted to the regulatory bodies or for publication. The purpose of investigator audits is to ensure that the investigator has maintained all study information according to the sponsor's protocol and standard operating procedures and in compliance with regulations.

The investigator will permit study-related monitoring, audits, and inspections by the EC/IRB, Stryker Orthopaedics and/or government regulatory bodies of all study related documents (e.g. source documents, regulatory documents, data collection instruments, study data). The investigator will ensure the capability for inspections of applicable study-related facilities.

11 Publication Plan

It is anticipated that publication of the multi-center study results of an observation period over two years, with optional five year period, will be compiled and submitted to a peer-reviewed journal. Additional publication proposals may be made by investigators at any time and will be considered.

This study will utilize the guidelines for authorship published by the International Committee of Medical Journal Editors (ICMJE). This guidance can be referenced at www.icmje.org.

Publications will be facilitated by the Chair and the primary investigator (PI) of the study. Both individuals will be chosen by Stryker Orthopaedics.

The PI is solely focused on the multi-center publications and progress towards those publications, including recurring updates to centers, center motivation as well as authorship. If the PI does not

produce a draft of a publication within 90 days of receiving the results data, Stryker Orthopaedics will delegate the responsibility to other investigators in the study at its discretion.

The Chair reviews all additional publications proposed by participating investigators based upon the study results prior to study completion, on an ongoing basis. This review includes whether or not a proposal will be pursued, as well as imposition of guidelines as to publication completion and criteria.

The following summarizes the possible roles of these parallel positions:

Chair	PI
Contributes to study design	Contributes to study design
Assists with study questions requiring expert clinical opinion	Assists with study questions requiring expert clinical opinion
Reviews additional publication proposals submitted by investigators	Updates investigators on progress towards multi-center results
Contributing author, if ICMJE guidelines met	Primary author, multi-center publication of primary endpoint data

Table 5 Possible roles of chair and PI

At the completion of the study, each participating study investigator shall have independent publication privileges for his/her own center's results. Although Stryker will not be involved in coordinating these independent manuscripts, all publications of the data shall be submitted to Stryker for review prior to submission for publication. Stryker shall not edit or otherwise influence the publications other than to ensure that confidential information is not disclosed, that no off-label use of Stryker devices is promoted and that the data is accurately represented. Any publications resulting from this study must be submitted to Stryker for review at least 60 days prior to submission of publication.

12 Risk/Benefit Assessment

12.1 Risk Category, potential Risk

There are no additional risks associated as the study is a retrospective review.

12.2 Expected Complications and Rates of Occurrences

In the retrospective data review it can be expected to find known complications.

- Known complications after use of acrylate*:

Intraoperative:

Temporary drop in blood pressure immediately after application of cement, pulmonary embolism and myocardial infarctions in rare cases.

Post-operative:

Temporary reduction in blood pressure, elevated blood serum levels diseases of the blood system, loosening of dislocation of the implant, wound infections, cardiovascular and pulmonary diseases, rare cases of anaphylaxis and sudden death.

- Known complications after use of PMMA**:

Allergic pyrexia, diseases of the urinary system, local neuropathy, vascular diseases, irritation of the sciatic nerve.

- Known complications causing from Simplex HV with Gentamicin:

Hypersensitivity reactions, typical side effects of using Gentamicin which are extremely unlikely to occur because of the very low serum level of Gentamicin.

For more details see “Adverse event” sections of IFU in **Appendix D**.

* Liquid, see **Tables 2 and 3**

** Powder, see **Tables 2 and 3**

12.3 Potential Benefits to the Subject

There is no guarantee that subjects will personally benefit from the retrospective data review within this study. This study seeks to provide clinicians information about Simplex HV bone cement. Information gathered in this study may benefit others undergoing TKA using Simplex HV bone cement in the future.

13 Ethical Considerations

This study is to be conducted for the protection of human subjects according to international standard ISO 14155 and applicable regional government regulations.

This protocol and any amendments will be submitted to a properly constituted independent EC/IRB for formal approval of the study conduct. The decision of the EC/IRB concerning the conduct of the study will be made in writing to the investigator and a copy of this decision will be provided to Stryker Orthopaedics before commencement of this study. The investigator may be asked to provide a list of EC/IRB members and their affiliates to Stryker Orthopaedics, if available. An EC/IRB confirmation will be applied for waiver of patient information and informed consent due to collection of pseudonymized retrospective patient data.

14 Study Finances

14.1 Funding Source

This study is financed by Stryker.

14.2 Conflict of Interest

Any investigator who has a conflict of interest with this study (e.g. patent ownership, royalties or financial gain greater than the maximum allowable by their institution) must have the conflict reviewed by their EC/IRB or a properly constituted Conflict of Interest Committee with a Committee-sanctioned conflict management plan that has been reviewed and approved by Stryker prior to participation in this study.

Appendix A Component Listing

Study Device Component Listing:

Catalogue Number
Simplex HV Plain (non-medicated)
6189-1-010
Simplex HV Gentamicin
6193-1-010

Ancillary Component Listing:

Triathlon Cemented Primary Tibial Baseplate
5520-B-100
5520-B-200
5520-B-300
5520-B-400
5520-B-500
5520-B-600
5520-B-700
5520-B-800

Triathlon Symmetric Conventional Polyethylene Patella
5550-L-278
5550-L-298
5550-L-319
5550-L-339
5550-L-360

Triathlon Symmetric X3 Patella
5550-G-278
5550-G-298
5550-G-319
5550-G-339
5550-G-360
5550-G-278-E
5550-G-298-E
5550-G-319-E
5550-G-339-E
5550-G-360-E

Triathlon Asymmetric Conventional Polyethylene Patella
5551-L-299
5551-L-320
5551-L-350
5551-L-381
5551-L-401

Triathlon Asymmetric X3 Patella
5551-G-299
5551-G-320
5551-G-350
5551-G-381
5551-G-401
5551-G-299-E
5551-G-320-E
5551-G-350-E
5551-G-381-E
5551-G-401-E

Triathlon CR Cemented Femur
5510-F-101
5510-F-102
5510-F-201
5510-F-202
5510-F-301
5510-F-302
5510-F-401
5510-F-402
5510-F-501
5510-F-601
5510-F-701
5510-F-801
5510-F-802

Triathlon PS Cemented Femur
5515-F-101
5515-F-102
5515-F-201
5515-F-202
5515-F-301
5515-F-302
5515-F-401
5515-F-402
5515-F-501
5515-F-601
5515-F-701
5515-F-801
5515-F-802

Triathlon CR Conventional Polyethylene Tibial Inserts
5530-P-X09
5530-P-X10
5530-P-X11
5530-P-X12
5530-P-X13
5530-P-X14
5530-P-X16
5530-P-X19

Triathlon CR X3 Tibial Inserts
5530-G-X09
5530-G-X09-E
5530-G-X10-E
5530-G-X11
5530-G-X11-E
5530-G-X12-E
5530-G-X13
5530-G-X13-E
5530-G-X14-E
5530-G-X16
5530-G-X16-E
5530-G-X19
5530-G-X19-E

Triathlon CS Conventional Polyethylene Tibial Inserts
5531-P-X09
5531-P-X10
5531-P-X11
5531-P-X12
5531-P-X13
5531-P-X14
5531-P-X16
5531-P-X19
5531-P-X22

Triathlon CS X3 Tibial Inserts
5531-G-X09
5531-G-X09-E
5531-G-X10-E
5531-G-X11
5531-G-X11-E
5531-G-X12-E
5531-G-X13
5531-G-X13-E
5531-G-X14-E
5531-G-X16
5531-G-X16-E
5531-G-X19
5531-G-X19-E
5531-G-X22-E
5531-G-X25

Triathlon PS Conventional Polyethylene Tibial Inserts
5532-P-X09
5532-P-X10
5532-P-X11
5532-P-X12
5532-P-X13
5532-P-X14
5532-P-X16
5532-P-X19
5532-P-X22

Triathlon PS X3 Tibial Inserts
5532-G-X09
5532-G-X09-E
5532-G-X10-E
5532-G-X11
5532-G-X11-E
5532-G-X12-E
5532-G-X13
5532-G-X13-E
5532-G-X14-E
5532-G-X16
5532-G-X16-E
5532-G-X19
5532-G-X19-E
5532-G-X22-E
5532-G-X25

X= size 1,2,3,4,5,6,7 and 8

Appendix B Case Report Forms

Title page

Simplex HV Bone Cement

A Retrospective Multicenter Study to Review the
Use of Simplex High Viscosity Bone Cement
in Primary Total Knee Arthroplasty

[figure not shown]
stryker®

Study # 80

Patient code (Use AA, BB,...AB)	

		

			Patient ID	

8	0	

Study #		

	8	0	Study #		

			

Center#			

				Center#			

			

Subject #			

				Subject #			

		

Side (L/R)		

			Side (L/R)	
8	0																											
Study #																												
Center#																												
Subject #																												
Side (L/R)																												

Stryker®		Simplex HV Retrospective Study					
Page 1 of 1		INCLUSION / EXCLUSION			Patient ID		
		8 0		Study#	Center#	Subject#	Side (L/R)
GENERAL INFORMATION							
Patient code (Use AA, BB,...AB)				Date of examination		 D D M M M Y Y Y Y	
I. INCLUSION CRITERIA							
Yes No							

A.   The patient is aged 18 years and over at time of study device implantation.
 
B.   Patients who have undergone primary Triathlon Total Knee Arthroplasty in which Simplex HV/ Simplex HV Gentamicin was indicated for fixation and used on label.
 
C.   Patients who have been followed for at least 24 months postoperatively
							
All of the above must be answered "Yes" for the patient to be enrolled in the study.							
II. EXCLUSION CRITERIA							
Yes No							

A.   Patients who have undergone revision surgery
 
B.   Patients who have undergone bilateral Knee Arthroplasty
 
C.   Patients contraindicated for either the devices implanted, or the cement used, according to medical history review and instructions for use.
 
D.   Patient has a cementless tibial baseplate.
 
E.   Patient has an active or suspected latent infection in or about the affected knee joint
 
F.   Patient has muscle loss or neuromuscular impairment in the affected limb that would create an unjustifiable risk.
 
G.   Patient is immunologically suppressed or receiving steroids in excess of normal physiological requirements (e.g. > 30 days)
 
H.   Patient has a known hypersensitivity to any of the cements constituents or in patients with severe renal failure
 
I.   Patient is a prisoner.
							
All of the above must be answered "No" for the patient to be enrolled in the study.							
III. Comments							

							
Investigator Name (Print)				For Stryker Use Only		INITIAL/DATE:	
Investigator Signature				Stamp Date Received:		Monitored: /	
Date		 D D M M M Y Y Y Y				Receipt: /	
						Entry: /	
						Verification: /	

Stryker® Simplex HV Retrospective Study												
Page 1 of 1			PRE-OP / DEMOGRAPHICS			Patient ID			8 0			
									Study#	Cont#	Subject#	Side (L/R)
GENERAL INFORMATION												
Patient code (Use AA, BB,...AB)						Date of examination						
									D D	M M M	Y Y Y Y	
DEMOGRAPHICS												
Age		Height		Weight		BMI		Gender				
								 male	 female			
DIAGNOSIS												
Patient's Initial Diagnosis						Operative side						
 Osteoarthritis			 Post Traumatic Arthritis			 left			 right			
PREOPERATIVE MEDICAL HISTORY (Relevant concurrent medical condition and treatment)												
Specify disease						Specify treatment						
 Gastrointestinal tract/metabolism			 No treatment			 Treatment						
 Blood and blood forming organs			 No treatment			 Treatment						
 Cardiovascular system			 No treatment			 Treatment						
 Skin			 No treatment			 Treatment						
 Reproductive system			 No treatment			 Treatment						
 Endocrine system			 No treatment			 Treatment						
 Infections and Infestations			 No treatment			 Treatment						
 Malignant/Immune disease			 No treatment			 Treatment						
 Muscles, bones and joints			 No treatment			 Treatment						
 Brain and nervous system			 No treatment			 Treatment						
 Respiratory system			 No treatment			 Treatment						
 Other			 No treatment			 Treatment						
 Other			 No treatment			 Treatment						
Investigator Name (Print)						For Stryker Use Only			INITIAL/DATE:			
						Stamp Date Received:			Monitored:	/		
									Receipt:	/		
									Entry:	/		
									Verification:	/		
Investigator Signature												
Date												
									D D	M M M	Y Y Y Y	

Stryker® Simplex HV Retrospective Study			
Page 1 of 1	Knee Society Score	Patient ID 8 0	
		Study#	Center#
		Subject#	Side (L/R)
GENERAL INFORMATION			
Patient code (Use AA, BB,...AB)		Date of examination 	
Pre-op visit 	Follow-up at  12-24 months (+2 months) post study surgery  5 years (± 3 months) post study surgery, specify  years  months		

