Evaluation	Pre-operative	Intra-operative	24 (+2) months post-operative	27 months up to 5 years post-operative
Inclusion/Exclusion	x			
Demographics & Medical History	x			
KSS	x		x	optional
Surgical Details		x		
Implant and Cement Details		x		
OKS	x		x	optional
A/P and Lateral X-ray Interface			x	optional
Adverse Events		x	x	per protocol

Table 1 Evaluation Schedule

1 Introduction

This document is a protocol for a retrospective human research study. This study will be conducted in compliance with the protocol, international standard ISO 14155 Standards, associated Federal regulations and all applicable research requirements.

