5.1 Inclusion/Exclusion Criteria

Inclusion Criteria:

- A. The Patient is age 18 or over at time of study device implantation
- B. Patients who have undergone primary Triathlon Total Knee Arthroplasty in which Simplex HV/Simplex HV Gentamicin was indicated for fixation and used on label
- C. Patients who have been followed for at least 24 months postoperatively

Exclusion Criteria:

- A. Patients who have undergone revision surgery
- B. Patients who have undergone bilateral Knee Arthroplasty
- C. Patients contraindicated for either the devices implanted, or the cement used, according to medical history review and instructions for use
- D. Patient has a cementless tibial baseplate.
- E. Patient has an active or suspected latent infection in or about the affected knee joint
- F. Patient has muscle loss or neuromuscular impairment in the affected limb that would create an unjustifiable risk
- G. Patient is immunologically suppressed or receiving steroids in excess of normal physiological requirements (e.g. > 30 days)
- H. Patient has a known hypersensitivity to any of the cements constituents or in patients with severe renal failure
- I. Patient is a prisoner

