5.4 Post-operative Data Collection

Data collection at 24 months (+ 2 months) postoperatively and optional at 5 years postoperative.

- Knee Society Score (KSS)
- Oxford Knee Score (OKS)
- X-ray collection for independent analysis
 - A/P view
 - Lateral view
- Elective surgery since study surgery
- Post-operative Adverse event or device deficiency

6 Adverse Events

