7.1 Definition of Aseptic Loosening

X-rays will be collected at least at two years after surgery for independent analysis of radiolucency occurrence at implant-cement interface by an independent reviewer

[figure not shown]
- Radiolucency at implant-cement interface
 - Tibia A/P
 - Tibia lateral
 - Femur PS lateral or Femur CR lateral

Radiolucencies at the implant-cement interface more than 2 mm in all zones of a component is defined as aseptic loosening.

[figure not shown]
Zones Tibia A/P⁷

Zones Tibia Lateral⁷

Zones Femur PS Lateral⁷

Zones Femur CR Lateral⁷

[figure not shown]

Figure 2 Component zones

8 Data Management

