9.1 Study Objectives

9.1.1 Objective Analysis

To evaluate the success rate of cemented Triathlon Total Knee components implanted using Simplex high viscosity bone cement (Simplex HV). Success is defined as absence of revision of cemented Triathlon Total Knee components implanted with Simplex HV for aseptic loosening at two years postoperative. 95% confidence interval of the success rate will be presented as well.

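### The follow-up CRFs offer one 12-to-26-month box for the visit that the protocol sets at 24 (+2) months, and no analysis window keeps month-12 scores and films out of the 24-month summaries

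*Combined protocol and SAP*

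**What the plan says.** The protocol text places the main post-operative assessment at 24 to 26 months. The Table 1 column for KSS, OKS, X-ray and adverse events is "24 (+2) months post-operative". Section 5.4 has "Data collection at 24 months (+ 2 months) postoperatively and optional at 5 years postoperative". Section 7.1 says "X-rays will be collected at least at two years after surgery for independent analysis". Inclusion criterion C in Section 5.1 admits "Patients who have been followed for at least 24 months postoperatively". Section 9.1.1 defines success as absence of revision "for aseptic loosening at two years postoperative".

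The forms in Appendix B differ. The KSS, OKS and Follow-up CRFs each carry the box "12-24 months (+2 months) post study surgery" and have no separate 24-month box. The label recurs on the second printed copies of the KSS and OKS forms, so it is not an isolated misprint. The Follow-up form puts the X-ray date and the aseptic-loosening question under the same box.

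For the optional later visit, Table 1 has "27 months up to 5 years post-operative" and the CRFs have "5 years (± 3 months) post study surgery, specify".

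Section 9.4.1 says that data not directly supporting an objective are summarized by follow-up. It defines no window for a follow-up. Section 9.3 rules out imputation.

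**The concern.** The study abstracts routine-care records (Section 4.1), so a site can enter only the visits that its own practice produced. If the nearest OKS, KSS or film is from month 12, the form invites entry in the same box as a true 24-month record. A monitor comparing the CRF with source would find them in agreement and need not raise a query. A summary grouped by the box would then mix assessments up to 14 months apart and present them as the 24-month result.

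Inclusion criterion C does not prevent this. It fixes how long the patient was followed, not when the score or film was taken. A knee with 24 months in the file can still have its only post-operative OKS at month 12.

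What is at stake is the meaning of the OKS, KSS and radiographic results and, under a further condition, the primary success rate.

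**Working it through.** The plan states no figure on this point, so there is nothing to reproduce. The check compares the windows and then bounds the effect on the primary endpoint.

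**1. Main visit**

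| Source | Window (months) |
|---|---|
| Table 1; Section 5.4 | 24 to 26 |
| Section 7.1 (films) | 24 or later |
| KSS, OKS and Follow-up CRFs | 12 to 26 |

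The protocol window is 26 − 24 = 2 months wide and the CRF window is 26 − 12 = 14 months wide. The part of the CRF window before month 24 is 12/14 = 86%. That is a share of the window, not of patients. The documents do not say how many knees were seen early.

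**2. Is there a rule in Section 9 that separates early records?** No. Section 9.1.1 covers only the primary objective. The by-follow-up sentence in Section 9.4.1 is the nearest rule for scores and films, and the only main follow-up category on the forms is the 12-to-26-month box. The rule against imputation does not remove a month-12 score from a 24-month table.

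**3. Worst case for the primary endpoint.** Assume that there is no file search, that event status is frozen at the visit, that the hazard is constant over 24 months, and that the 24-month risk is R = 5%. Let p be the share of knees frozen at month 12. All of these are assumptions.

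- Risk at 12 months: R12 = 1 − √(1 − R) = 1 − √0.95 = 2.53%.
- Share of events missed: p × (R − R12)/R = p × (5.00 − 2.53)/5.00 = p × 0.494.
- Apparent failure rate: (1 − p) × R + p × R12.

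| p | Events missed | Apparent failure (true 5%) |
|---|---|---|
| 25% | 12% | 4.38% |
| 50% | 25% | 3.77% |
| 100% | 49% | 2.53% |

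With R = 1% or 2% and p = 50%, the apparent rates are 0.75% and 1.50%. The share missed is therefore again about a quarter, and it hardly depends on R.

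**4. Late visit.** Table 1 leaves months 26 to 27 in no column. It then runs from 27 to 60 months, while the CRF box covers 60 ± 3, that is 57 to 63. A 36-month record fits Table 1 but not the CRF box. A 62-month record fits the CRF but exceeds Table 1.

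**The case against.** The strongest reply is that the primary endpoint is already protected. A reader might infer from the label that revisions in months 12 to 24 go uncounted and that the success rate is inflated. The documents do not support that as a general consequence:

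- Criterion C requires 24 months of follow-up, so month 24 has already passed for every eligible knee when the chart is read.
- Section 6.1 has staff search the hospital files for any doctor visit or hospitalization, and adverse events are reportable from surgery to the last follow-up specified in the protocol.
- The adverse event form carries its own start date and a revision date, independent of the visit box.
- Section 9.4.1 gives the two-year rate by Kaplan-Meier. Censoring a knee at month 12 costs precision but does not by itself favour success. Bias needs early status to be carried forward, and nothing instructs that.

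This stands to a large extent. What remains is narrow. Section 9.1.1 describes a success rate without naming Kaplan-Meier. The loosening question sits under the 12-to-26-month box. The forms have no field for last confirmed implant status, and no rule says that a negative answer dated before month 24 is not a 24-month success.

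It is also fair to say that the 24 (+2) window is a collection schedule. The primary endpoint is stated at 24 months or two years without the extra two months, and the secondary objective gives no time point. Examination and film dates are recorded, so early records can be found. This makes the repair easy, but the plan does not say to use those dates to assign visits.

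On the late visit, the assessment is optional, the CRF label agrees with Section 5.4, and the KSS and OKS forms have year and month fields for the actual time. That part is minor.

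**Conclusion.** The plan is wrong as written on this point. The forms contradict Table 1, Section 5.4 and Section 7.1, and Section 9 does not resolve the conflict. OKS, KSS and film summaries are directly exposed, because month-12 records can be pooled into the 24-month results. This conclusion rests on the text alone. The number of knees affected is unknown.

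The primary success rate is exposed only conditionally, if an early negative answer is taken as 24-month status. The 12%, 25% and 49% figures are a worst case with no file search. They rest on a constant hazard, an assumed 5% risk and assumed shares of 25%, 50% and 100%, none of which the documents give. They should not be read as an estimate of bias in this study.

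The late-window mismatches are real but secondary.

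**What to change.** 1. **CRFs.** Relabel the box on the KSS, OKS and Follow-up forms to the protocol's 24 (+2) months. Record anything earlier as a separate time point.
2. **Section 9.** State that visits are assigned by the interval from surgery date to examination or film date. State that earlier data are reported separately and not pooled into 24-month summaries. State that the primary event is scored from the revision date, with censoring at the date of last confirmed implant status.
3. **Minor.** Reconcile the optional late window across Table 1, Section 5.4 and the CRFs, and close the gap between 26 and 27 months.

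The cost is a form relabelling and a few lines of text. Surgery, examination, film and revision dates are already collected; the date of last confirmed implant status has no field of its own and would have to be added or derived from the file. The downside is that fewer knees will have a qualifying 24-month score or film, so the number contributing to each summary should be reported.
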